8.3.6.3. Acute Systemic Allergic Reactions

Grade 1 (Localized Urticaria [Wheals] With no Medical Intervention Indicated)

Participants may continue the intake of study interventions.

Cetirizine, levocetirizine, topical corticosteroids, or antipruritic agents may be prescribed.

Participants should be advised to contact the investigator immediately if there is any worsening of the acute systemic allergic reaction.

Grade 2 (Localized Urticaria With Intervention Indicated, or Mild Angioedema With no Intervention Indicated)

Participants may continue the intake of study interventions.

Cetirizine, levocetirizine, topical corticosteroids, or antipruritic agents may be prescribed.

Participants should be advised to contact the investigator immediately if there is any worsening of the acute systemic allergic reaction, in which case the participant will permanently discontinue the intake of JNJ-3989. Rechallenge is not allowed. The participant's NA treatment may be discontinued based on investigator judgement in consultation with the sponsor.

Grade 3 (Generalized Urticaria, Angioedema With Intervention Indicated, or Symptoms of Mild Bronchospasm) and Grade 4 (Acute Anaphylaxis, Life-Threatening Bronchospasm, or Laryngeal Edema)

Participants will permanently discontinue the intake of JNJ-3989. Rechallenge is not allowed. The participant's NA treatment may be discontinued based on investigator judgement in consultation with the sponsor.

Participants will be treated as clinically appropriate. Participants should be followed until resolution of the AE and standard management should be undertaken.

8.3.6.4. Renal Complications

If renal complications develop, participants should be closely monitored for disturbances in creatinine clearance. Additional investigations can be performed at the investigator's discretion. Participants must be treated as clinically appropriate.

Participants who develop confirmed Grade 3 or 4 eGFR abnormalities with reduction from baseline by at least 10 mL/min/1.73 m² will permanently discontinue the intake of JNJ-3989, if the abnormality is considered at least possibly related to JNJ-3989, and should be followed appropriately until resolution of AE or toxicity. Rechallenge is not allowed. Change of NA treatment should be considered according to the prescribing information.

8.3.6.5. Hematologic Abnormalities

As already mentioned in Section 2.1, JNJ-3989 is also being developed in combination with JNJ-6379.

Mild thrombocytopenia was observed in recently conducted nonclinical toxicology studies with the combination of JNJ-3989 and JNJ-6379. In addition, in a 3-month combination study with 80 rats, 1 rat developed pancytopenia related to bone marrow depletion after 23 days of dosing. Previously, in a 9-month dog study in 24 dogs treated with JNJ-6379 alone, pancytopenia which correlated with a marked increase in plasma cell-like cells in the bone marrow was observed in 1 dog after 60 days of dosing.

Review of laboratory data in the REEF-1 study showed a low number of hematologic laboratory abnormalities and most were of Grade 1 or Grade 2 severity. Low absolute neutrophil count was most frequently reported in the JNJ-3989 (200 mg) + NA arm (Grade 1: 4 [4.3%] participants and Grade 2: 2 [2.1%] participants). Changes in hemoglobin and platelets in the JNJ-3989 + NA +/- JNJ-6379 arms were comparable to the Placebo + NA arm. Few hematologic laboratory abnormalities were also observed in the REEF-2 study (73763989PAHPB2002), which were balanced between the active and placebo arms. In the Phase 1/2a AROHBV1001 study with JNJ-3989, mild transient thrombocytopenia (Grade 1) was observed in 6 out of 84 participants receiving 3 SC injections of JNJ-3989 alone over a period of up to 12 weeks with background of NAs. The transient thrombocytopenia was not considered clinically significant. No thrombocytopenia or pancytopenia was observed in 12 participants when JNJ-3989 and JNJ-6379 were given in combination over a 12-week period.

As these findings were not clearly attributed to JNJ-3989, JNJ-6379, or the combination of the 2 study interventions, measures for close monitoring of hematological changes during the study are in place.

Any relevant abnormalities in hematologic parameters will be carefully monitored as described below:

- Platelet counts: $<100,000$ cells/mm³ or <100 GI/L or reduction from baseline by at least 50%
- Hemoglobin: Decrease of at least 2 g/dL from baseline or at least Grade 2 (DAIDS)
- Reticulocytes: Reduction to $<0.5\%$ of the RBC count
- Neutrophil count: Treatment emergent reduction to at least Grade 2 (DAIDS)

In case any one of the above criteria are met, a confirmatory visit should be scheduled as soon as possible, preferably within 7 days of the receipt of the initial results. Confirmation of the results will trigger weekly or biweekly (every other week) unscheduled visits until improvement or stabilization of the respective parameter(s). Stabilization is defined as no further significant reduction over 2 consecutive visits.

In case of confirmed Grade 3 or Grade 4 hematologic abnormalities, discontinuation of investigational study treatment (JNJ-3989) should be considered. In case of discontinuation, NA treatment should be continued.

8.3.6.6. Complications From Liver Biopsy

Participants should be closely monitored for liver biopsy complications. Infection and internal bleeding and/or puncture of other internal organs (gall bladder, lung, intestine or kidney) can lead to serious complications (uncommon 1 in 1,000 to 1 in 100) including the need for emergency surgery, blood transfusion or removal of organs. Deaths directly related to liver biopsy occur rarely (approximately 1 in every 10,000 biopsies). Criteria for participant selection and laboratory assessments are in place to minimize these risks. Additional investigations can be performed at the investigator's discretion. Participants must be treated as clinically appropriate.

8.4. Pharmacokinetics

Sparse PK samples for JNJ-3989 will be collected in all participants according to the [Schedule of Activities](#).

Plasma samples will be used to evaluate the PK of JNJ-3989 (JNJ-73763924 and JNJ-73763976). Plasma collected for PK may additionally be used to evaluate safety or efficacy aspects that address concerns arising during or after the study period, or for analysis of plasma concentrations of co-medications.

8.4.1. Evaluations

Venous blood samples will be collected for measurement of plasma concentrations of JNJ-3989 (JNJ-73763924 and JNJ-73763976), at time points specified in the [Schedule of Activities](#).

8.4.2. Analytical Procedures

Pharmacokinetics

At the sponsor's discretion, a selection of plasma samples will be analyzed to determine concentrations of JNJ-3989 (JNJ-73763924 and JNJ-73763976), using a validated, specific, and sensitive liquid chromatography-mass spectrometry method or liquid chromatography fluorescence method, as applicable, by or under the supervision of the sponsor.

Plasma PK samples may be stored for future exploratory analysis of protein binding or the metabolite profile. Genetic analyses will not be performed on these plasma samples. Participant confidentiality will be maintained.

To allow selection of samples, the bioanalytical laboratory will receive randomization lists per IA and/or upon request of the bioanalytical scientist. Unblinding of the treatment code will be performed at the bioanalytical laboratory only and will be subjected to a procedure that will ensure that codes will not be revealed to anyone involved in the execution of the study.

8.4.3. Pharmacokinetic Parameters and Evaluations

Sparse PK samples for JNJ-3989 will be collected and plasma concentration-time data for JNJ-3989 (JNJ-73763924 and JNJ-73763976) will be analyzed. Data from this study may be combined with data from a selection of Phase 1 and 2 studies via population PK modeling. If performed, the population PK analysis will be described in a separate analysis plan and results will be reported separately.

8.5. Pharmacokinetics/Pharmacodynamics

Relationships of individual PK parameters for JNJ-3989 (JNJ-73763924 and JNJ-73763976) with selected efficacy and/or with selected safety endpoints may be evaluated, if applicable.

8.6. Immune Assessments

At selected sites, PBMC samples for immune analyses will be collected during study intervention and may be analyzed centrally for HBV-specific responses by enzyme-linked immunospot (ELISpot) and/or intracellular cytokine staining (ICS) after stimulation with HBV-specific antigens. ELISpot detects HBV-specific T-cells that secrete gamma interferon (IFN- γ) in response to a specific antigenic stimulation, whereas ICS determines the frequency of CD4+ and CD8+ HBV T-cells secreting cytokines such as IFN- γ , interleukin (IL)-2 and tumor necrosis factor (TNF)- α in response to a specific antigenic stimulation.

PBMC samples may also be analyzed for HDV-specific responses using ELISpot and ICS after stimulation with HDV-specific antigens.

Additional experiments may be performed to further phenotypically and functionally characterize PBMCs using proliferation or cytotoxic assays or other methods such as cytometry by time of flight to evaluate innate and adaptive immune responses. Leftover PBMC samples may be used at

the sponsor's discretion for additional exploratory research related to HBV or HDV infection or study intervention (safety/efficacy).

Additional PBMC samples may be taken until Week 48 in case of ALT flares, upon discussion with the sponsor, which may require an unscheduled visit.

8.7. Host Genetics

A pharmacogenomic blood sample will be collected from participants who consent separately to this component of the study to allow for pharmacogenomic research, as deemed necessary (where local regulations permit).

An optional pharmacogenomic (host DNA) blood sample may be collected (preferably at baseline) to allow for host pharmacogenomic research, where local regulations permit. Complete host genomic testing may be done to search for links of specific genes to (HBV/HDV-related) liver disease or to the PK, PD, efficacy, safety, or tolerability of the study intervention. These samples will only be collected from participants who consent separately to this component of the study. Further, a participant may withdraw such consent at any time without affecting their participation in other aspects of the study.

In addition, other samples may be used for exploratory genetic research in participants consenting separately to this part of the study. No host DNA research will be performed on any sample in participants who have not provided the additional separate consent for host genetic research. Samples can only be used to investigate the potential association of host genetic factors with efficacy, safety, or PK of study intervention, or HBV or HDV infection, or may be used to develop tests/assays related to study intervention or HBV or HDV infection.

8.8. Host Biomarkers

The study includes collection of blood samples for exploratory analysis of host blood biomarkers (eg, cytokines) at the host RNA, protein, and cell level. Exploratory serology samples, which will be collected in all participants at the time points indicated in the [Schedule of Activities](#), may be used for this host serum protein testing.

Blood samples will be taken at the time points indicated in the [Schedule of Activities](#) which can be used to explore immunogenicity of JNJ-3989. The emergence of antibodies to JNJ-3989 (antidrug antibodies) might be analyzed using assays such as an enzyme-linked immunosorbent assay.

Samples can only be used for research related to study intervention or HBV or HDV infection or may be used to develop tests/assays related to study intervention or HBV or HDV infection.

8.9. Medical Resource Utilization

Medical resource utilization data, associated with medical encounters, will be collected in the CRF by the investigator and study-site personnel for all participants throughout the study. Protocol-mandated procedures, tests, and encounters are excluded. The data collected may be used to conduct exploratory economic analyses and will include:

- Number and type of medical visits (eg, in/out hospital, ER visit).
- Number (proportion) of participants requiring hospitalization and duration of hospitalization (total days length of stay, including duration by wards; eg, ICU).
- Number and character of diagnostic and therapeutic tests and procedures (inpatient and outpatient).

9. STATISTICAL CONSIDERATIONS

Statistical analysis will be done by the sponsor or under the authority of the sponsor. A general description of the statistical methods to be used to analyze the efficacy and safety data is outlined below. Specific details will be provided in the SAP.

The primary analysis in this study will be performed when all participants in the study (both parts if Part 2 has started) have reached Week 48 or have discontinued earlier.

The final analysis will be performed when all participants in the study (both parts if Part 2 of the study has started) have reached the final study visit in the follow-up phase, or have discontinued earlier.

9.1. Statistical Hypotheses

The original protocol had as primary hypothesis of this study that the combination regimen of JNJ-3989 + NA has superior efficacy compared to NA treatment alone in reducing HDV replication and improving the associated liver inflammation, as measured by the primary efficacy endpoint at Week 48 (the proportion of participants with HDV RNA decline $\geq 2 \log_{10}$ IU/mL from baseline or HDV RNA TND in combination with normal ALT at Week 48). Due to the decision to stop enrollment at 30 participants in Part 2 of the study (see Section 9.2), the statistical analyses will be descriptive.

9.2. Sample Size Determination

The sample size in Part 1 (N = 20) is primarily driven by the objectives of Part 1 to provide sufficient evidence of safety and early antiviral activity of JNJ-3989 and to exclude futility of the regimen in a small number of HBV/HDV co-infected participants before initiating the larger Part 2 of the study. No formal statistical power calculations were conducted for Part 1.

A total sample size of 130 participants for Part 2 in the original protocol would yield a statistical power >90% to detect a between-arm difference of $\geq 26\%$ in the primary efficacy endpoint at Week 48, at a 1-sided Type 1 error rate of 0.025, based on the test for the between-arm difference

in proportions with the normal approximation. Per Protocol Amendment 4, the sample size in Part 2 was reduced to 30 participants.

In the original protocol, sample size re-estimation was planned at the single IA during Part 2 to allow for an increase to a maximum of 170 participants in Part 2 for the conditional power at the end of the study to be at least 80% in case the assumed 0.04 response rate for placebo was too conservative. Due to reduction in sample size per Protocol Amendment 4, the single IA with sample size re-estimation was removed.

In the original protocol, the number of participants included in this study was planned to be a minimum of approximately N 20 (if Part 2 is not initiated) or between a minimum of N 165 and a maximum of N 190 if Part 2 is initiated. Per Protocol Amendment 4, the planned number of participants included in the study will be N 20 in Part 1 and N 30 in Part 2.

9.3. Participant Analysis Sets

For purposes of analysis, the following analysis sets are defined:

Analysis set	Description
Screened	All participants who signed the ICF.
Randomized	All participants who were randomly assigned to an intervention arm in the study.
Intent-to-treat (ITT)	All participants who were randomly assigned to an intervention arm and who received at least 1 dose of study intervention. Participants will be analyzed according to the study intervention they were randomly assigned to.
Modified intent-to-treat (mITT)	All participants who were randomly assigned to an intervention arm and who received at least 1 dose of study intervention, excluding those participants impacted by the COVID-19 pandemic, defined as those participants who, because of COVID-19 or similar pandemic-related reasons, withdrew prematurely from the study prior to Week 48, or had no efficacy assessment for the primary endpoint. COVID-19 or similar pandemic-related reasons may include for example missed visits due to travel restrictions, shortage of lab kits at the planned visit, missed collection of blood sample at key time points for the primary efficacy endpoint, etc. Participants will be analyzed according to the study intervention they were randomly assigned to.
Safety	All participants who take at least 1 dose of study intervention. Participants will be analyzed according to the study intervention they actually received.

9.4. Statistical Analyses

The SAP will be finalized prior to study start and will include a more technical and detailed description of the statistical analyses described in this section.

9.4.1. General Considerations

The primary analysis set for efficacy will be the ITT set (defined in Section 9.3). All efficacy summaries will be presented with descriptive statistics by intervention arm by study Parts 1 and 2, as well as for the whole study data overall.

If the endpoint is continuous, the descriptive statistics will include the number of participants, mean, standard deviation (SD), median, range and interquartile range. If the endpoint is binary or categorical, the frequency distribution with the number and percentage of participants in each

category will be calculated. For time-to-event variables, a summary table including number of participants included in the analysis, number of participants censored, 25th and 75th percentiles and median time-to-event will be shown by intervention arm. Graphic displays will also be used to summarize the data. Summaries will also be presented by presence of compensated cirrhosis at screening (yes or no).

The baseline measurement is defined as the assessment taken the closest to but before the first administration of study intervention on Day 1.

9.4.2. Primary Endpoint

The primary efficacy endpoint is defined as the proportion of participants with HDV RNA $\geq 2 \log_{10}$ IU/mL decline from baseline or HDV RNA TND in combination with normal ALT levels at Week 48.

9.4.2.1. Primary Estimand

The main analysis of the primary endpoint will be addressed by using the following estimand attributes:

1. Study Intervention:

- Arm 1: JNJ-3989 + NA
- Arm 2: Placebo + NA

2. Study population: Participants 18 to 65 years of age, inclusive, with HBV/HDV co-infection

3. Variable: Response status defined as having HDV RNA decline $\geq 2 \log_{10}$ IU/mL from baseline or HDV RNA TND in combination with normal ALT at Week 48

4. Intercurrent events (ICEs):

- a. Treatment discontinuation prior to Week 48: if the participant discontinued treatment prior to Week 48 then the participant will be considered as non-responder (composite strategy).
- b. Selected major protocol deviations (identified as ICEs): participants who experienced major protocol deviations considered ICE and who have missing ALT and/or HDV RNA data for the primary endpoint at Week 48 will be considered as non-responders (composite strategy).
- c. Deaths prior to Week 48 are handled in a composite strategy as participants who die prior to Week 48 will be considered as non-responders.

5. Population level summary: Difference in proportion of responders between the 2 intervention arms (Arm 1-Arm 2).

Note: The SAP will list the major protocol deviations used for the purpose of efficacy analyses and flag those that are to be considered ICEs.

Assumptions:

- Missing Data for HDV RNA and ALT are Missing At Random (MAR)
- The treatment effect is homogeneous across strata.

Data Included

All available data from randomized participants that have received at least one dose is included (ITT analysis set in Part 2), after taking into account all the ICEs and applying the ICE strategies.

Missing Data Handling Rules

Participants who withdraw from the study prior to Week 48 will be considered as non-responders.

If a participant remains in the study after early discontinuing treatment or after experiencing a major protocol deviation (defined for the purpose of efficacy analyses and is an intercurrent event) and has missing Week 48 value for HDV RNA and/or ALT, then the imputation to non-response will be applied. If the value for the primary endpoint at Week 48 is available, then such data will be used to determine their response status.

For the participants still in the study at Week 48 or for participants that have neither discontinued treatment early nor experienced any major protocol violations (defined for the purpose of efficacy analyses and is an intercurrent event), and, either HDV RNA or ALT values are missing at Week 48, the primary method to handle missing data will be the Multiple Imputation (MI) approach, applied in a joint multivariate fashion to leverage the correlation between HDV RNA and ALT values over time. More details regarding the multiple imputation multivariate model will be included in the SAP.

To challenge and assess the impact of the MAR assumption in presence of intercurrent events, different approaches to handle missing data will be used as sensitivity analyses of the main estimator. Two sensitivity analyses will be conducted with different rules to handle missing HDV RNA and/or ALT values at Week 48. One sensitivity analysis will be based on the tipping point approach based on the Missing Not At Random (MNAR) assumption, and the other analysis will use a single imputation method. For the latter, the Last Observation Carried Forward (LOCF) in conjunction with the next available observation imputation approach will be used. The non-missing value closest to Week 48 will be selected among the non-missing values for HDV RNA and/or ALT which are no earlier than 12 weeks prior or no later than 4 weeks post Week 48. If both HDV RNA and ALT values are missing at Week 48, the imputed values will be chosen at the same timepoint. If 2 non-missing laboratory values are equidistant, the later observation will be preferred.

As a supplementary estimator, the analysis where all participants with missing HDV RNA and ALT values in the analysis window of Week 48 in each arm are imputed as non-responders will be conducted to provide a comprehensive overview of the robustness for the assumption of MAR and the type of missing data.

The main estimator and statistical model are discussed in the next section. The estimator will be presented for Part 2 data as well as for the whole study data.

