7.2. Participant Discontinuation/Withdrawal From the Study

A participant will NOT be automatically withdrawn from the study if he or she has to discontinue study intervention.

A participant will be withdrawn from the study for any of the following reasons:

- Lost to follow-up
- Withdrawal of consent
- Death

When a participant withdraws before study completion, the reason for withdrawal is to be documented in the CRF and in the source document. If the reason for withdrawal from the study is withdrawal of consent then no additional assessments are allowed.

Withdrawal of Consent

A participant declining to return for scheduled visits does not necessarily constitute withdrawal of consent. Alternate follow-up mechanisms that the participant agreed to when signing the consent form apply as local regulations permit.

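### The primary estimand makes every early treatment stopper a non-responder, but the missing-data rules let an available Week 48 value decide

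*Protocol*

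**What the plan says.** Section 9.4.2.1 lists three intercurrent events, all labelled as composite.

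- **Item 4a, treatment discontinuation:** "if the participant discontinued treatment prior to Week 48 then the participant will be considered as non-responder (composite strategy".
- **Item 4b, selected major protocol deviations:** non-response applies only where ALT or HDV RNA is also missing at Week 48.
- **Item 4c, death before Week 48:** non-response.

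The missing-data rules follow. Anyone who withdraws from the study before Week 48 is a non-responder. The next rule covers a participant who stays in the study after stopping treatment early, or after a deviation that counts as an intercurrent event. If that participant "has missing Week 48 value for HDV RNA and/or ALT, then the imputation to non-response will be applied". The sentence after it reads: "If the value for the primary endpoint at Week 48 is available, then such data will be used to determine their response status".

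The following paragraph opens "For the participants still in the study at Week 48 or for participants that have neither discontinued treatment early nor experienced any major protocol violations" and says that, where HDV RNA or ALT is missing at Week 48, "the primary method to handle missing data will be the Multiple Imputation (MI) approach".

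The synopsis (Section 1.1) repeats these rules. Section 9.4.3 says that the key secondary endpoints are handled in a similar fashion.

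**The concern.** Item 4a is a composite strategy: stopping treatment is itself the failure. The available-value sentence is in effect a treatment-policy strategy: stopping is ignored and the Week 48 measurement decides. These are different estimands, and the protocol applies both to the same people under one primary endpoint.

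The case can arise. Section 7.2 says: "A participant will NOT be automatically withdrawn from the study if he or she has to discontinue study intervention". Under footnote a of Section 1.3.1, participants who stop early enter follow-up, where Section 1.3.3.1 schedules HDV RNA and liver function tests.

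It may also fall unevenly on the arms. ALT/AST elevations are a ground for stopping (Section 7.1), and all 12 Part 1 participants with on-treatment ALT elevations up to Week 48 were on JNJ-3989 (Section 2.2.3).

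In a descriptive study the response proportions are the result, so they need one definition.

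**Working it through.** The protocol gives no figure for this point, so the check is to run each kind of early stopper through the stated rules.

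| Participant who stops treatment before Week 48 | Item 4a | Missing-data rules |
|---|---|---|
| In study, Week 48 values present, criterion met | Non-responder | Responder |
| In study, Week 48 values present, criterion not met | Non-responder | Non-responder |
| In study, Week 48 value missing | Non-responder | Non-responder by the express rule; multiple imputation on a literal reading of the next paragraph |
| Withdrawn from the study or died before Week 48 | Non-responder | Non-responder |

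Row 1 is the substantive conflict. Row 3 is a secondary wording error. The multiple-imputation paragraph joins its two groups with 'or', so its first group takes in anyone still in the study at Week 48, including an early stopper whom the preceding paragraph has already set to non-response.

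**Effect of one reclassified participant.** Section 4.1 gives approximate Part 2 arm sizes of 24 and 6; Section 2.2.3 gives 17 on JNJ-3989 in Part 1.

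- Part 2, Arm 1: 1/24 = 4.2 points.
- Part 2, Arm 2: 1/6 = 16.7 points.
- Part 1, Arm 1: 1/17 = 5.9 points.

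**Illustration for Part 2, Arm 1.** Let d be the number of early stoppers still in the study with Week 48 values, and q the proportion of them who meet the criterion. Assume that 30% of the other 24 − d respond. The values of d, q and 30% are assumptions; the protocol supplies none of them for Part 2.

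- Rate under item 4a = 0.30 × (24 − d)/24.
- Rate under the available-value rule = the same + d × q/24.

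| d | Item 4a | q = 0 | q = 0.10 | q = 0.25 | q = 0.50 |
|---|---|---|---|---|---|
| 4 | 25.0% | 25.0% | 26.7% | 29.2% | 33.3% |
| 8 | 20.0% | 20.0% | 23.3% | 28.3% | 36.7% |

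If no early stopper meets the criterion, the two rules agree.

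**Do the planned sensitivity analyses cover it?** No. The tipping-point analysis, the carried-forward or next-observation analysis and the missing-as-failure analysis all vary the handling of missing values. Row 1 concerns observed values.

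**The case against.** The best defence is one of precedence. Under Data Included, data enter after the intercurrent-event strategies have been applied, so item 4a would act first. Item 4b alone is conditioned on missing data, so the available-value sentence fits 4b naturally. This is a sensible reading and probably the intended one. It does not remove the conflict, because the available-value sentence follows directly on one that names participants who stopped treatment early. On the precedence reading it has no effect for them. Item 4b also shows that the authors wrote a missing-data condition where they meant one, so 4a cannot be assumed to contain it.

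On multiple imputation the defence is stronger. The express non-response rule agrees with 4a, and 'or' was probably meant as 'and'. That limb is a wording correction only.

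Deferral to the SAP does not settle the matter. Section 9.4.2.1 defers the imputation model and the list of deviations, but states both discontinuation rules itself.

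A fair caution is that choosing a rule now is a choice made after unblinding. The amendment history records a treatment-policy strategy for selected events at Amendment 1 and a clarification of the estimand at Amendment 2, so the available-value sentence may be a leftover. That is a reason to disclose which rule was pre-specified and to show both results.

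**Conclusion.** The contradiction between item 4a and the available-value sentence stands, in Section 9.4.2.1 and in the synopsis, and it carries over to the key secondary endpoints. The 'or' in the multiple-imputation paragraph is a lesser drafting error. Severity is should-fix: Section 9.1 makes the analyses descriptive, so no confirmatory test depends on this.

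The size is 4.2 points per reclassified participant in Part 2 Arm 1 and 16.7 in Arm 2, taking the approximate arm sizes as 24 and 6. The total shift is unknown and may be small. In Part 1, all 4 responders on JNJ-3989 were among the 5 participants there without ALT elevations (Section 2.2.3), although that report does not say which rule classified them.

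A reader might infer more, but the document does not support it:

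- **That a large share of Part 2 is affected.** The participant status in the Amendment 5 rationale gives no stopping dates. Those no longer in the open-label phase may include people who stopped after Week 48, or placebo participants not rolled over under Section 7.1.
- **That the week of stopping fixes whether a Week 48 value exists.** The protocol does not give the width of the Week 48 analysis window. Follow-up visits may be anchored to the last dose, the last planned treatment visit or the withdrawal visit.
- **That the shift should be judged against the original design difference.** That difference belongs to the abandoned 130-participant design.
- **That the sponsor will choose the rule after seeing results.** Section 9.4 says that the SAP is finalized before study start. Nothing shows such a choice.

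**What to change.** 1. In Section 9.4.2.1, limit the available-value sentence to protocol-deviation events under item 4b. Any stop of treatment before Week 48 is then non-response whether or not a value exists, as item 4a states.
2. In the multiple-imputation paragraph, replace the 'or' between the two groups with 'and', so that imputation applies only to participants still in the study at Week 48 who have neither stopped treatment early nor had a qualifying deviation.
3. Make the same two edits in the synopsis, and confirm that the key secondary endpoints follow the same rule.
4. Report the available-value version as a labelled supplementary treatment-policy analysis.
5. Because participants are already unblinded, state which rule was pre-specified in the SAP, or used if the analysis has been run. Show both results, with the number of early stoppers per arm whose classification differs.

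The cost is two sentences edited in two places and one additional table. No new data are needed. The Arm 1 rate under the composite rule can only be equal to or lower than under the available-value rule.
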